## **ADVERSE EVENT REPORTING**

An adverse event (AE) is any untoward medical occurrence in a patient or clinical study participant, temporally associated with the use of study treatment, whether considered related or not related to the study treatment. Adverse events will be collected during Visits 2 and 3.

A serious adverse event (SAE) is any untoward medical occurrence that:

- Results in death
- Is life-threatening
- Requires Participant hospitalization or prolongs the post-treatment hospitalization
- Results in persistent or significant disability or incapacity
- Causes a congenital anomaly in the offspring of the Participant, or
- Is considered an important medical event that jeopardizes the health of the Participant or requires surgical intervention to prevent one of the outcomes listed above

Any serious adverse events associated with use of the Investigational device will be submitted to the IRB in writing within 24 hours of learning about the SAE. Reportable new information will be reported to the IRB per the institutional policy.

## **7.0 RISK/BENEFIT**

In accordance with the company's Risk Management Procedure, use-related risks were identified and evaluated prior to device design to develop design inputs and risk mitigation. Additional use-related risks were identified and evaluated, and risk reduction measures implemented for them during device development and testing. As a result, residual risk (post-risk-reduction) has been reduced to acceptable levels.

## NON-SIGNIFICANT RISK DETERMINATION

A significant-risk (SR) device study is defined by the United States Food and Drug Administration (<https://www.fda.gov/media/75459/download>) as one that:

- Is intended as an implant *and* presents a potential for serious risk to the health, safety, or welfare of a subject;
- Is purported or represented to be for use supporting or sustaining human life and presents a potential for serious risk to the health, safety, or welfare of a subject;
- Is for a use of substantial importance in diagnosing, curing, mitigating, or treating disease, or otherwise preventing impairment of human health and presents a potential for serious risk to the health, safety, or welfare of a subject;
- or otherwise presents a potential for serious risk to the health, safety, or welfare of a subject.

A Non-Significant Risk (NSR) device study is one that does not meet the definition for an SR device study. This study poses no significant risks, does not meet the definition above, and tests a device that is considered exempt from FDA clearance. The only “off label” use of the drain is the addition of low-level suction. The Sponsor has identified the following risks and mitigations to further explain the justification for the NSR determination:

## RISK & RISK MITIGATION

The following risks have been identified as “potential” based on similar devices:

- Perforation: The risk of perforation is mitigated by the placement of this drain under direct observation followed by an ultrasound confirming correct placement after closure. In addition, the drain is constructed of smooth, atraumatic materials.
- Endometritis: Endometritis is mitigated by selection of appropriate materials, selection of appropriate participants, and limited drain dwelling time. Endometritis can occur regardless of device use. To evaluate the occurrence of endometritis, participants will be followed out to the time of the post-partum visit.
- Vaginitis or tissue trauma: Vaginitis or tissue trauma is mitigated by using non-irritating materials and an atraumatic drain design. To evaluate for the occurrence of vaginitis or tissue trauma, participants will be followed out to the time of the post-partum visit.
- Infection: Infection is mitigated through the direction of drain placement, sterility of the drain, and limited time of exposure to the drain (~2.5 hours) in addition to careful participant selection.
- Loss of Participant Confidentiality: The principal risk of a signed consent document would be the potential harm resulting from a breach of confidentiality. Every precaution will be taken to minimize this. The original signed consent documents will be stored in the research office which will be locked when not attended. Electronic logs will be stored in password protected desktop computers, accessible only to the research team. Data will

be stored according to institutional policy. At any given time, there will be 1 to 3 people from the Sponsor and/or site's research team present to abstract data. De-identified data will be collected in the database which will be accessible to outside institution team members. Data transferred out of the site will be de-identified data with the study ID number. The key containing the study ID number with the participant information will be accessible to the study team only and will be stored securely on password-protected computers. No genetic information will be collected for this study.

**NOTE:** Participation in the study is not expected to alter the likelihood of occurrence or severity of any standard surgical risks at the time of the CD. There is no risk to the fetus since the drain is placed after birth. Other than drain placement/removal and addition of suction during placement, there are no changes to the standard operative procedures. Participants are unlikely to experience sensation of the drain placement because it will be placed and removed while the participant is still under the influence of the epidural or spinal anesthesia. There is a small risk of unintentional loss of confidentiality. All efforts will be made to minimize this risk. There are no anticipated emotional, psychological, economic, legal, or social risks to the participants associated with this study.

For these reasons, it is the opinion of the Sponsor that this study design poses no significant risk to the participant.

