The hysterotomy is then closed taking care not to loop any sutures around the drain. Blood flow through the lumen will be measured by attaching the suction tubing to a fluid collection container (e.g., bag, or calibrated suction canister). Tubing must be secured to the thighs using a foley catheter securing adhesive to avoid displacement before attaching to the suction canister. For this Protocol, 100mmHg of suction is recommended to induce uterine involution. The *DAISY* drain will remain in place for a minimum of 3 hours while the Participant is in the recovery unit. At the end of 2-hours, the uterus will be evaluated by manual palpation and abdominal ultrasound. The abdominal ultrasound will be performed to document device placement and to assess uterine involution, approximate uterine size and uterine cavity size, presence of intrauterine clots or retained products of conception. Following the ultrasound, the suction is to be reduced to 10mmHg for 5 minutes. After 5 minutes, the investigator will again assess uterine tone and perform another ultrasound. After the second ultrasound, the Daisy is left in place with the suction at 10mmHg for 30 minutes. After 30 minutes, the investigator is to again assess uterine tone manually and perform the third ultrasound.

NOTE: If the uterine cavity is assessed by ultrasound and/or clinically determined to contain clots or products of conception, the device will be removed after discontinuation of suction, the study participant discontinued, and management undertaken per institutional protocol. Thirty minutes before device removal, any suction applied must be discontinued to observe for any additional bleeding. Clinical management of the subject will determine the time for device removal, but the device must be removed within 24 hours of placement. [See “Instructions for Use” provided to the user.]

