#### **DAISY DRAIN Removal:**

The user who has undergone IFU training will remove the *DAISY* drain after at least two hours post CD based on clinical management. Suction will be discontinued, and the participant observed for 30 minutes before removal. One method of determining if the *DAISY* drain is no longer needed is by checking and documenting uterine tone. If uterine tone has returned to normal as assessed by palpation, the *DAISY* drain may be removed. (Note: If the uterine tone has not returned to normal, the user may choose to leave the drain in place and resume suction.) Upon drain removal, suction is briefly reapplied to collect any blood in the lumen after the 30-minute resting period. **Suction must be discontinued before the drain is removed.** Placing one hand on the abdomen to support the uterus while the other hand slowly withdraws the drain, the person removing the drain will evaluate the ease of drain removal. [See “Instructions for Use” provided to the user.]

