**APPENDIX 1**  
**DEVICE USE QUESTIONNAIRE**

Surgeon Name: \_\_\_\_\_

Obstetrician

Fellow

Resident (Circle one)

Years of experience in Obstetrical Surgery: \_\_\_\_\_

Date of Evaluation: \_\_\_\_\_ Placement #: 1 2 3 (Circle One)

Type of Suction Tube used (Brand & ID): \_\_\_\_\_

This Questionnaire aims to evaluate a set of aspects related to the use of the Daisy® device by the personnel in attendance. You are asked to indicate your level of agreement for each of the questions posed below, according to the scale of responses, place a check mark in the appropriate box.

	Strongly Agree	Agree	Neutral	Disagree	Strongly Disagree
Device training clearly explained insertion, use and removal of the device.					
The Instructions for Use (IFU) are clear and concise.					
The Daisy was easy to insert through the cervix.					
The Daisy was easy to properly position within the uterus.					
The Daisy was easily visualized in the lower uterine segment at time of placement.					
The Tube of the Daisy was easily advanced through the vaginal canal.					
The Cap of the Daisy was easily identified & retrieved outside the introitus.					
The Cap of the Daisy was easy to remove from the Tube.					
The Cap of the Daisy had adequate retention in the Tube.					
The Daisy did not interfere with the closure of the hysterotomy incision.					
The Daisy Tube fits easily into standard suction tubing.					

The suction tubing was easy to secure to the leg of the participant using the provided adhesive Catheter Anchors.					
The Daisy remained in place until elective removal.					
The estimated blood loss from the uterus was easy to determine.					
Use of the Daisy did not interfere with routine OR or PACU practices.					
The force to remove the Daisy was acceptable.					
Overall, the Daisy was easy to use.					
The Daisy drained without intervention (clot removal). Describe any clots or interventions in the Comments below.					
Blood flow was easy to visualize through the Tube.					
Overall, the Daisy met all the user needs as intended.					

Other comments regarding the use of the Daisy: \_\_\_\_\_

\_\_\_\_\_

\_\_\_\_\_

\_\_\_\_\_

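### The risk section says the drain is removed under epidural or spinal anesthesia, but the protocol's removal window does not secure this and no data field would let it be checked

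*Protocol*

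**What the plan says.** The NOTE that closes the risk list in Protocol section 7.0 tells the reader that sensation from the drain is unlikely, because "it will be placed and removed while the participant is still under the influence of the epidural or spinal anesthesia". The NOTE then gives the sponsor's opinion that the design poses no significant risk, and presents it as following from the reasons just listed. The protocol mentions this anesthesia nowhere else.

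The timing of removal is described in several places:

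- Section 5.0, Device Description: the "drain will remain in place for a minimum of 3 hours while the Participant is in the recovery unit". The same section says "Clinical management of the subject will determine the time for device removal" and adds that "the device must be removed within 24 hours of placement".
- Section 5.0, DAISY Drain Removal: the trained user takes out the "drain after at least two hours post CD based on clinical management". If uterine tone is not back to normal, the user may keep the drain in and restart suction.
- Section 7.0, infection risk: the mitigation relies on "limited time of exposure to the drain (~2.5 hours").
- Section 6.0, Visit Schedule: removal is placed in the recovery room.

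On measurement, the removal item in the Appendix 1 questionnaire is the surgeon's rating of the statement "The force to remove the Daisy was acceptable". Appendix 2 lists insertion time, removal time and adverse events. It has no item for type of anesthesia, state of the block, participant-rated pain, or analgesia given for removal.

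**The concern.** The sentence on anesthesia is unconditional and covers removal as well as placement. It is offered as a property of the design. Yet the sections that govern removal set the time by uterine tone and clinical judgment, allow the dwell to be extended, and never refer to the block. The reviewing board is asked to accept a premise that the schedule does not enforce.

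What is at stake is modest but real. Discomfort at removal is a harm that the protocol itself raises and then sets aside on this premise. Ease of removal is a named evaluation item in section 6.0, and it is judged by the person removing the drain. If removals occur late in the permitted window, the final report could describe removal as easy without being able to say whether the participant still had an effective block.

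**Working it through.** **1. The plan's own minimum.** Inputs are the steps in section 5.0, Device Description, in minutes.

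| Step | Minutes | Running total |
|---|---|---|
| Suction until first assessment | 120 | 120 |
| Reduced suction until second assessment | 5 | 125 |
| Reduced suction until third assessment | 30 | 155 |
| Suction off before removal | 30 | 185 |

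185 / 60 = 3.08 h, or 3 h 05 min, before any time for the palpation and scans themselves. This agrees with the stated 3-hour minimum (185 − 180 = 5 min over).

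**2. The other lower bounds.** The removal subsection read alone gives 120 min, or 120 + 30 = 150 min = 2.5 h if the observation period follows the two hours. The latter matches the 2.5 hours cited under infection risk. Without the suction-off period, the section 5.0 steps give 155 min = 2.58 h. So the protocol carries three lower figures: 2 h, about 2.5 h and 3 h. They do not share a clock either. The two hours run from the cesarean, while the 3-hour minimum concerns time in place, and the drain goes in before the uterus is closed. The protocol gives no length for that gap.

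**3. The upper bound.** 24 h = 1,440 min. 1,440 / 180 = 8 times the 3-hour minimum, and 1,440 / 150 = 9.6 times the exposure cited in the risk section.

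**4. What the assurance requires.** Let R be the time from placement to removal and B the time from placement until the block wears off. The sentence is true for a participant only if R ≤ B.

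- To hold for every permitted removal, it needs either a rule that keeps R ≤ B, or B of at least 24 h. The protocol states neither.
- To fail for every participant, B would have to be shorter than the earliest R. The protocol gives no value of B, so this cannot be shown either.

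**5. Can the data test it?** Appendix 2 holds both insertion and removal times, so R can be calculated for each participant. It holds nothing on the block, so the comparison of R with B cannot be made. An adverse event or a comment might record pain, but silence would not establish that pain was absent or that the block was working.

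**The case against.** The best reply is that the risk section is written around about 2.5 hours of exposure and that the Visit Schedule puts removal in the recovery room. On this view the anesthesia sentence describes the expected case, and the 24-hour limit is only an outer bound. The wording is also hedged, since it says sensation is unlikely. Part of this stands: early removal in the recovery room is plainly what the authors had in mind, and a removal many hours later on a ward is a permitted possibility that the protocol does not describe. But a recovery room is a location and not a block status, and it does not override the clinical discretion, the option to resume suction or the 24-hour limit.

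Other parts of the reply also stand.

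- A reader might infer that the assurance is false, by assuming a usual duration for a spinal block. The documents give no duration and also name epidural anesthesia, so only the weaker statement is supported.
- A reader might infer that pain at removal goes unrecorded altogether. Adverse events are collected at Visit 2, which includes removal; company staff initially observe removals and gather feedback; and the questionnaire has free-text comments. What is missing is a dedicated item.
- A reader might infer that the permitted window starts firmly at 3 hours. It does not, as the conflicting figures show.
- A reader might infer that the non-significant-risk determination collapses. The determination turns on the potential for serious risk and rests on several reasons. Transient discomfort would not by itself overturn it.
- The study is stated to focus more on users than on participants, and no objective concerns comfort. The extra fields are thus a recommendation that supports a claim the protocol chose to make. They do not repair a missing endpoint.

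**Conclusion.** The point holds in a limited form. Section 7.0 states as fact something that the removal provisions do not secure: three different lower figures (2, about 2.5 and 3 hours, with the section 5.0 steps summing to 3 h 05 min), a 24-hour limit, discretion over timing, and no link to the block. The assurance is not guaranteed over the permitted window, and the planned data cannot confirm it. This conclusion uses only the protocol's own timings and assumes nothing about how long a block lasts. It affects the accuracy of the risk statement and the tolerability information from 10 participants. It does not invalidate the study. It should be corrected before the risk statement is relied on.

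**What to change.** Reconcile section 5.0 (Device Description and DAISY Drain Removal), the Visit Schedule in section 6.0, and the infection item and closing NOTE in section 7.0, so that the risk statement matches the removal window the protocol permits. Which timing is adopted is for the sponsor and investigators; this review does not propose one. If the risk wording given to participants repeats the claim, align it as well. The consent text is not in view, so whether it does is unknown.

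Add three items to Appendix 2, recorded at removal: neuraxial block still effective (yes/no), participant-rated pain on a 0–10 scale, and any analgesic given for removal. Report them descriptively alongside each participant's dwell time, calculated from the insertion and removal times already collected. With 10 participants, a listing is enough and no subgroup comparison is warranted.

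The cost is one wording amendment, a few fields for 10 participants including one question at removal, and possibly a slightly less favourable risk statement.

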#### **POTENTIAL BENEFITS TO PARTICIPANTS**

There is no proven direct benefit to participants in this study of the *DAISY* drain. Although similar devices have shown positive outcomes, benefits to participants in this study cannot be guaranteed.

## **8.0 DATA MANAGEMENT AND STATISTICAL ANALYSIS**

The data collected will be marked with a study ID number to protect the confidentiality of each Participant. Only the research staff will have access to the link between the study ID and the patient's identifying information. The key will be stored in a password-protected document on a restricted access folder on the hospital network. Only the Principal Investigator, Sub-Investigator, and research team will have access to this document. This document will contain the participants' de-identified obstetric and medical history as relevant for the project.

Third-party data management and statistical analysis of de-identified data may be used. Analysis of the user responses will consist primarily of means, medians, and standard deviations. To accomplish this, the following points will be assigned to user responses.

Strongly Disagree 1 point	Disagree 2 points	Neutral 3 points	Agree 4 points	Strongly Agree 5 points
------------------------------	----------------------	---------------------	-------------------	----------------------------

The Sponsor will follow up with any responses where the user has "disagreed" or "strongly disagreed" with the statement.

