## **6.0 STUDY DESIGN AND METHODOLOGY**

This is a prospective, single-arm, device evaluation study of five (5) obstetrical surgeons placing the drain with low-level suction in ten (10) women undergoing elective, non-emergent cesarean delivery.

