## **NUMBER OF USERS & PARTIPANTS**

In this study, 5 (five) users will place the *DAISY* drain in ten (10) participants do not have any of the contraindications for drain use at the time of the CD. Each user will place the drain at least once but no more than three times. After each obstetrical surgeon uses the *DAISY* drain, they will be asked to complete a questionnaire (Appendix 1).

The *DAISY* drain and Instructions for Use (IFU) will be evaluated qualitatively for the following including:

- ease of drain placement by obstetrician-surgeon
- appropriate size of drain
- appropriate final location of the deployed drain and incidence of improper placement
- ease of drain connection to suction tubing
- ease of drain removal
- perceived effectiveness of suction
- clarity of the IFU

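### Section 8 summarises device events as agreement scores, so the named means, medians and SDs give no event rate

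*Protocol*

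**What the plan says.** Section 6.0 describes a single-arm "device evaluation study of five (5) obstetrical surgeons placing the drain with low-level suction in ten (10) women". Under Number of Users & Participants it adds: "Each user will place the drain at least once but no more than three times". A questionnaire follows use of the drain. The form carries the surgeon's name and a placement number from 1 to 3, so it is read here as one form per placement, ten in all.

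Section 8.0 says of the answers: "Analysis of the user responses will consist primarily of means, medians, and standard deviations". It continues: "To accomplish this, the following points will be assigned to user responses". The scale runs from 1 (strongly disagree) to 5 (strongly agree). The sponsor will follow up every answer in the two negative categories. Section 8.0 names no count or proportion and does not say whether the unit of summary is the placement or the surgeon.

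Most Appendix 1 items ask for a judgement, such as ease of insertion. Two ask what happened: "The Daisy remained in place until elective removal" and "The Daisy drained without intervention (clot removal". Both are answered on the agreement scale; the second also asks for clots or interventions to be described in the comments. The Section 6.0 list of aspects to be evaluated includes how often the drain is improperly placed.

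**The concern.** Whether a drain came out early, or needed a clot removed, has a yes or no answer at each placement. The useful summary is how many of the ten placements had the event. Section 8.0 instead places these items on the same footing as opinions and names three statistics, none of which is a count. The Section 6.0 aim of an incidence of improper placement likewise has no matching summary.

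At stake is what the report conveys. With ten placements, one or two failures are a 10% or 20% event rate, which matters to a sponsor judging the device. The same data can appear as a mean above 4 and a median at the top of the scale. Part of the problem also arises at data collection. A 1-to-5 answer can be split into two groups later, but a neutral answer to a factual statement has no clear meaning once the case is over.

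**Working it through.** The protocol gives no figure to reproduce: it states no hypothesis test, power or sample-size calculation. The check asks what the Section 8.0 statistics show when events occur.

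**Inputs.** Ten placements by five surgeons, one to three each (Section 6.0); scores 1 to 5 (Section 8.0). The score patterns below are illustrations, not data.

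**1. Failures scored 1, all other placements scored 5.** Mean = sum/10; SD = √(sum of squared deviations/9).

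- One failure: mean = (9×5 + 1)/10 = 4.6. SD = √[(9×0.4² + 3.6²)/9] = √(14.4/9) = 1.26. Median 5.
- Two failures: mean = (8×5 + 2×1)/10 = 4.2. SD = √[(8×0.8² + 2×3.2²)/9] = √(25.6/9) = 1.69. Median 5.
- Three failures: mean = (7×5 + 3×1)/10 = 3.8. SD = 1.93. Median still 5.

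**2. Can the event count be read back from the three statistics?** Not reliably.

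- Six 5s and four 4s, with no failure at all: mean = (30 + 16)/10 = 4.6, median 5, SD = √[(6×0.4² + 4×0.6²)/9] = √(2.4/9) = 0.52. The mean and median match the one-failure case; only the SD differs.
- Two failures scored 2 with eight 5s: mean = (40 + 4)/10 = 4.4, median 5, SD = √[(8×0.6² + 2×2.4²)/9] = √(14.4/9) = 1.26. The SD and median match the case of one failure scored 1.

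So the SD signals that answers disagree, but does not say how many events there were.

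**3. An event rated neutral.** One 3 with nine 5s: mean = 48/10 = 4.8, median 5, SD = √[(9×0.2² + 1.8²)/9] = √(3.6/9) = 0.63. The answer is in neither negative category, so the follow-up rule does not apply.

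**4. The same information as counts.** Exact (Clopper-Pearson) 95% intervals for x/10:

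| Events | Proportion | Exact 95% CI |
|---|---|---|
| 0/10 | 0% | 0 to 30.8% |
| 1/10 | 10% | 0.3 to 44.5% |
| 2/10 | 20% | 2.5 to 55.6% |

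**5. Forms per surgeon.** If a surgeons place once, b twice and c three times, then a + b + c = 5 and a + 2b + 3c = 10, which gives a = c. The only possible splits are 2-2-2-2-2, 3-2-2-2-1 and 3-3-2-1-1. In the last, two surgeons supply 6 of the 10 forms. This is a reason to list answers by surgeon; it does not show that a summary over forms is wrong.

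**The case against.** The strongest reply is that failures are already picked up case by case. The sponsor follows up every negative answer, and both failure examples use scores of 1. Sponsor staff observe users (Sections 6.0 and 9.0), and the clot item asks for a description. Appendix 2 collects insertion and removal times and ultrasound device position at three time points. The SD, at 1.26 or 1.69 on a 1-to-5 scale, would alert a careful reader. Section 8.0 says its statistics are used primarily, not exclusively, and an analysis plan that is not shown may add counts. Appendix 2 lists primary data and is not the case report form itself, so the absence of a field from that list does not prove that none exists. Finally, no decision threshold depends on an interval for x/10.

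Much of this stands. Failures rated negatively would not go unnoticed, and improper placement can probably be counted from the ultrasound data. But follow-up is not a commitment to report a count, and it misses a neutral rating. An analysis plan can add a table; it cannot change how the questionnaire puts the two event items. The interval is there to show how little ten placements can exclude, which needs no threshold.

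A reader might go further and infer that Section 8.0 pools ten forms as if independent, over-weights surgeons with three placements, and so overstates the information. The text does not support that. It does not state the unit. Unequal weighting cannot arise with two placements each, and equal weight per placement is a legitimate choice if the target is the average use of the device. An SD describes spread and does not shrink as forms are added. The protocol names no standard error, confidence interval or test for these scores, so design effects and effective sample sizes bear on nothing it plans.

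**Conclusion.** The point holds for the event items and for improper placement. The only statistics that Section 8.0 names for user responses do not yield event rates: one or two failures in ten can leave the mean at 4.6 or 4.2 and the median at 5. These sizes rest on failures being scored 1 and all other placements 5; other patterns give other values.

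For the opinion items, means and medians are acceptable but should not stand alone, because surgeons may contribute one to three forms each. The documents give no ground for requiring the surgeon to be the sole unit of analysis.

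Severity is minor. The study is descriptive, and no error rate, power or sample size is affected.

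**What to change.** - **Questionnaire or case report form:** record as yes or no, for each placement, whether the drain stayed in place until elective removal and whether it drained without clot intervention. Keep the free-text description of clots.
- **Section 8.0, events:** report these two events and improper placement as x/10 placements with exact 95% intervals, and state what counts as improper placement. The intervals treat placements as independent, so a footnote should say that some share a surgeon.
- **Section 8.0, opinion items:** beside the mean and median, show the count in each of the five response categories, with a listing by surgeon and placement number. Both identifiers are already on the form.

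The cost is two tick-boxes, a few sentences in Section 8.0 and a slightly longer table. The tick-boxes should be in place before the first form is completed, because a neutral answer to an event item may not be resolvable afterwards.
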